6. ANALYSES AND SUMMARIES

Point estimates and 95% confidence intervals will be provided for each of the PF-04965842 QD treated groups (200 mg and 100 mg) and placebo.

A summary of analyses for clinical efficacy endpoints is provided in Appendix 1. Visit windows to be used for all efficacy analyses and some relevant safety analyses are detailed in Appendix 2.

Data collected at Week 16 will be displayed in listings only, and will not be part of any analyses, unless specifically noted otherwise.

6.1. Primary Endpoint

The primary endpoints in this study include mean fold-changes for the following biomarkers:

- General inflammation (MMP12);

- Hyperplasia (K16);
- Th2 (CCL17, CCL18, CCL26);
- Th22 (S100A8, S100A9, S100A12).

6.1.1. Primary Analysis

- Summary: Fold-change from baseline at Week 12;
- Population: FAS;
- Statistical Method: Estimate and 95% CI from MMRM described in [Section 5.2.1](#);
- Missing Data: No explicit imputation.

6.1.2. Additional/Supportive Analysis

- Summary: Fold-change from baseline at Week 12;
- Population: PPAS;
- Statistical Method: Estimate and 95% CI from MMRM described in [Section 5.2.1](#);
- Missing Data: No explicit imputation.

6.2. Other Biomarker Endpoints

The other biomarker endpoints in this study include mean fold-changes for the following biomarkers:

- epidermal thickness (performed on H&E sections);
- Ki 67+ cells,
- Keratin 16 (K16);
- **CCI** [REDACTED]
- [REDACTED]
- [REDACTED]
- [REDACTED]
- [REDACTED]

- CCI [REDACTED]
- [REDACTED]

6.2.1. Primary Analysis

- Summary: Fold-change from baseline at Week 12;
- Population: FAS;
- Statistical Method: Estimate and 95% CI from MMRM described in [Section 5.2.2](#);
- Missing Data: No explicit imputation.

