The primary objective of this study is to assess the effects of abrocitinib on lesional and non-lesional skin biomarkers of adult participants with moderate-to-severe AD. The following estimand attributes will be considered:

- Population: Participants with moderate-to-severe AD as defined by the inclusion criteria;
- Variable: Fold-change from baseline in the biomarkers for general inflammation (MMP12), hyperplasia (K16), type 2 helper T cell (Th2) immune response (CCL17,

CCL18, CCL26), and type 22 helper T cell (Th22) immune response (S100 calcium binding protein A [S100A8], S100A9, S100A12);

- Intercurrent event: All data collected will be utilized;
- Population-level summary: Mean fold-change from baseline within each treatment group.

Overall Design:

This is a randomized, double-blind, placebo-controlled, parallel-group, Phase 2a study to investigate the mechanism of action of abrocitinib by correlating efficacy outcomes with changes from baseline in key skin and blood biomarkers in adult participants ≥ 18 years of age with moderate-to-severe AD. Participants will be screened within 28 days prior to the first dose of study intervention to confirm study eligibility. A total of approximately 51 participants will be randomized in a 1:1:1 ratio to receive abrocitinib 200 mg once daily (QD), abrocitinib 100 mg QD, or matching placebo QD for 12 weeks.

The double-blind treatment period will last from Baseline/Day 1 to Week 12. Lesional skin biopsy (punch biopsy) collections are required at Baseline/Day 1 (Week 0), Day 29 (Week 4), and Day 85 (Week 12), with an optional lesional skin biopsy collection at Day 15 (Week 2). Non-lesional skin biopsy collection is required at Baseline/Day 1 (Week 0), with an optional non-lesional skin biopsy collection at Day 85 (Week 12).

The skin biopsy samples will be analyzed using immunohistochemistry (IHC) and gene expression by quantitative reverse transcriptase polymerase chain reaction (qRT-PCR), including Taqman Low Density Array (TLDA) PCR, for 48 genes including 2 housekeeping genes (18S and ribosomal protein lateral stalk subunit P0 [RPLP0]), as well as single gene PCR for a few genes that are often below detection level on TLDA. CCI

Blood for analyses of changes in inflammatory and cardiovascular markers will be collected at various time points. CCI

Red

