2.2.2. Phase 2b in AD (B7451006)

B7451006 was a Phase 2b proof-of-concept trial in 269 adults (ages 18-75) with moderate-to-severe AD investigating doses of 10, 30, 100, and 200 mg abrocitinib or placebo taken once daily for up to 12 weeks. The primary endpoint was the proportion of participants achieving an Investigator's Global Assessment (IGA) score of clear (0), or almost clear (1), and a ≥ 2 -point improvement from baseline at Week 12. The baseline was defined as the IGA score on Day 1 pre-dose.

At Week 12, IGA response rates of the abrocitinib 200 mg and 100 mg dose groups were significantly greater than the placebo group, 44.5%, 27.8% and 6.3%, respectively. As a result, the estimated differences from placebo in the 200 mg and 100 mg groups were 38.2% ($P=0.0032$) and 21.5% ($P=0.0184$), respectively. The percent change from baseline in Eczema Area and Severity Index (EASI) scores at Week 12 were significantly higher for both the 200 mg and 100 mg groups compared to placebo, 63.7%, 41.6%, and 15.6% respectively. At Week 12, the proportion of participants achieving EASI-75 response was 15.6% in the placebo group, 63.7% in the 200 mg group and 41.6% in the 100 mg group. As a result, the difference from placebo was 41.8% ($P<0.0001$) for the 200 mg group and 26.0% ($P=0.0043$) in the 100 mg group. Response rates at Week 12 for the 10 mg and 30 mg groups were not significantly different from placebo.

At Day 15, the proportion of response based on achieving Peak Pruritus numerical rating scale 4 points improvement from baseline (NRS4) of abrocitinib 100 mg and 200 mg dose groups was greater than placebo. The estimated proportion of Peak Pruritus NRS4 responses at Day 15 were 69.8%, 41.1% and 15.7% for 200 mg, 100 mg and placebo groups, respectively.

Abrocitinib demonstrated a rapid onset of action. In the 200 mg group, IGA and EASI scores improved until Week 4 and Week 6, respectively, and maintained their effect through 12 weeks of treatment. A key differentiating feature for the JAK1 inhibitor is rapid resolution of itch associated with AD. Significant separation from placebo was achieved for the Peak Pruritus numerical rating scale (NRS) score as early as 2 days after initiation of treatment for the 200 mg dose group.

Overall, the results demonstrated dose dependent increases in responses at Week 12 for key efficacy endpoints (IGA, EASI and Peak Pruritus NRS).

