The double-blind treatment period will last from Baseline/Day 1 to Week 12. For all participants, one 4.5 mm skin biopsy (punch biopsy) will be collected from each target treatment area at the specified time points. Lesional skin biopsies will be collected at Baseline/Day 1 (Week 0), Day 29 (Week 4), and Day 85 (Week 12), with an optional lesional skin biopsy collection at Day 15 (Week 2). A non-lesional skin biopsy will be collected at Baseline/Day 1 (Week 0), with an optional non-lesional skin biopsy collection at Day 85 (Week 12). **CCI**

Biopsy samples will be used to perform gene expression by quantitative reverse transcriptase polymerase chain reaction (qRT-PCR), including Taqman Low Density Array (TLDA) PCR, for 48 genes including 2 housekeeping genes (18S and RPLP0), as well as single gene PCR for a few genes that are below detection level on TLDA (see [Table 1](#)). **CC1**

Immunohistochemistry (IHC) analysis will be performed for cellular infiltrates, Keratin 16 (K16) staining, and hematoxylin and eosin (H&E) staining.

Many of the genes to be analyzed in this study are considered key biomarkers associated with AD pathways. For this study, the following biomarkers were selected for the primary endpoint: general inflammation (MMP12), hyperplasia (K16), Th2 immune response (CCL17, CCL18, CCL26), and Th22 immune response (S100A8, S100A9, S100A12).

CC1

The efficacy outcomes (eg, IGA, EASI, % body surface area [%BSA], and peak pruritus numerical rating scale [PP-NRS]) are collected so that any associations between biomarker changes and these efficacy outcomes may be evaluated. The clinical improvement will be correlated with the suppression of individual immune pathways, cellular infiltrates, and changes in epidermal biomarkers. Differences between groups and changes from baseline will be estimated. Tests of hypotheses for differences between treatment groups will not be performed.

Safety will be assessed by physical exams, standard laboratory testing, and collection of AEs.

Refer to the [Schedule of Activities](#) for a complete list of assessments to be performed during the study.

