3.2. Secondary Endpoints

The secondary endpoints are:

- Changes from baseline in gene expression (evaluated by mRNA PCR and/or gene arrays) over time in skin lesions;
- Changes from baseline in cellular (T cells and dendritic cells) markers using IHC in skin biopsies at various time points;
- Changes from baseline in hyperplasia markers (thickness, K16, Ki67) in skin biopsies;
- Changes from baseline in blood biomarkers (OLINK proteomic microassay for inflammation and immune response in serum);
- Changes from baseline in T cell lymphocyte subset populations in blood using flow cytometry;
- Change from baseline in IHC and genetic markers in lesional skin.

A detailed description of how the pruritus NRS score is derived is provided in Appendix 3.

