5.2.1. Analysis of Primary Endpoint

The population for the primary analysis will be all participants in the FAS having valid biomarker data at baseline and Week 12.

The primary endpoints in this study include mean fold-changes for the following biomarkers:

- General inflammation (MMP12);
- Hyperplasia (K16);
- Th2 (CCL17, CCL18, CCL26);
- Th22 (S100A8, S100A9, S100A12).

In each participant, expression levels from RT-PCR will be normalized to the housekeeping gene RPLP0 (validated in other studies) by negatively transforming the Ct values to $-dCt$, obtaining an equivalent to log2 scale expression values (reporting unit: log2 [Expression/RPLP0]). The expression values below detection will be estimated for each gene as the 20% of the minimum of unlogged values across all samples (which is equivalent to subtracting 2.321928 from the $-dCt$ minimum value). The expression levels below detection may provide important information about some markers that significantly change with treatment (eg, the expression may decrease below the level of detection after treatment), therefore this imputation is an important step in the analysis.

RT-PCR expression data in log2 scale will be modeled using a mixed effect model with Treatment, Time Point, and Tissue Type as a fixed effect and a random intercept for each participant. This model will yield unbiased estimates and valid inferences in the presence of a missing data mechanism that is missing at random (MAR).¹ This approach introduces less bias than restricting the analysis for participants with complete observations. Contrasts will be used to estimate the log2 fold-changes for each treatment group. Fold-changes will be computed by obtaining the antilog of log2 fold-changes. Point estimates and 95% confidence intervals (CIs) will be obtained for the fold-change from baseline in the biomarker values for each treatment group based on this model.

Correlation analyses will be performed to assess if the fold-change from baseline in biomarkers correlates with change (from baseline) in the clinical efficacy endpoints such as IGA, EASI, and Peak Pruritus NRS.

Supportive analyses for the primary endpoint will also be performed using the PPAS.

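### SAP 6.2.1 names Week 12 as the only summary time for the other skin biomarkers, although two secondary endpoints in SAP 3.2 are defined across several visits

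*SAP*

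**What the plan says.** SAP 3.2 lists the secondary endpoints. One is "Changes from baseline in gene expression (evaluated by mRNA PCR and/or gene arrays) over time in skin lesions". Another concerns T-cell and dendritic-cell "markers using IHC in skin biopsies at various time points". Protocol Section 3 words both the same way. The hyperplasia endpoint (thickness, K16, Ki67) names no time point.

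Protocol 4.1 fixes the tissue schedule: "Lesional skin biopsies will be collected at Baseline/Day 1 (Week 0), Day 29 (Week 4), and Day 85 (Week 12"). A further lesional sample at Week 2 is left to choice. The Synopsis describes the Baseline, Week 4 and Week 12 lesional biopsies as required.

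SAP 6.2.1 is the only analysis section for the other biomarkers in the visible text. It gives one summary, "Summary: Fold-change from baseline at Week 12", in the FAS, from the model in 5.2.2. SAP 6.1.1 and 6.1.2 use the same Week 12 summary for the eight primary genes.

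SAP 5.2.1 lists Treatment, Time Point and Tissue Type as fixed effects with a random intercept per participant. It says that contrasts will give fold-changes by treatment group, and it names no visit. It also restricts the primary population: "The population for the primary analysis will be all participants in the FAS having valid biomarker data at baseline and Week 12".

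**The concern.** A summary at one visit cannot deliver an endpoint defined over several. Elsewhere in section 6 the SAP names visits when it wants them: IGA and EASI responses at Weeks 2, 4, 8 and 12 (6.3.2, 6.3.3), and BSA and Night Time Itch at all scheduled visits (6.3.4, 6.4.2). Against that pattern, the lone Week 12 in 6.2.1 reads as a rule that conflicts with the endpoint definitions, not merely as missing detail.

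The study exists to relate tissue changes to clinical response. Protocol 2.2.2 reports from Phase 2b that "In the 200 mg group, IGA and EASI scores improved until Week 4 and Week 6, respectively", and that itch response already separated by dose at Day 15. Week 2 and Week 4 tissue is the only tissue that falls within that period of change. If no estimate for those visits is prespecified, the IGA and EASI results at Weeks 2 and 4 have no matching tissue result. Any early-visit biomarker estimate shown later would then have been chosen after the data were available. Participants also undergo an invasive procedure to supply these samples.

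**Working it through.** **1. Endpoint against output**

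| Secondary endpoint (SAP 3.2) | Timing in its definition | Timing in visible SAP section 6 |
|---|---|---|
| Gene expression in skin lesions | over time | Week 12 only (6.2.1), unless the supplementary biomarker SAP adds more |
| T-cell and dendritic-cell IHC markers | various time points | Week 12 only (6.2.1) |
| Hyperplasia markers | none named | Week 12 (6.2.1): no conflict |
| Primary endpoint, eight genes (SAP 3.1) | none named | Week 12 (6.1.1, 6.1.2): no conflict |

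The mismatch is confined to the first two rows.

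**2. Tissue affected**

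Inputs: about 51 participants (SAP 2.2); required lesional biopsies at Day 1, Week 4 and Week 12 (Protocol 4.1).

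- Required lesional biopsies: 51 × 3 = 153.
- Required post-baseline: 51 × 2 = 102.
- Week 4 share: 51 / 102 = 50%.
- With Week 2 uptake u, the share with no named summary is (51 + 51u) / (102 + 51u).

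The documents give no uptake. For assumed u = 25%, 50%, 75% and 100%, the share is 55.6%, 60.0%, 63.6% and 66.7%. All these counts are upper bounds, because they assume no dropout and no failed samples.

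**3. Could the early visits be estimated usefully?**

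The plan's own precision figure comes first. SAP 2.2 states about a 92% chance that the 95% CI half-width is at most 3.2, with n = 17 and SD 5.

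P(half-width ≤ h) = P(χ² with n−1 df ≤ (n−1) × [h√n / (t × SD)]²), where t is the 0.975 quantile on n−1 df.

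For n = 17, t = 2.120, so 3.2 × √17 / (2.120 × 5) = 1.245. Then 16 × 1.245² ≈ 24.8, and the probability is 92.6%. The stated figure reproduces. So does 3.2 / 5 = 64%.

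Week 4, with all 17 per arm sampled, has that same precision. Week 2 depends on uptake, so n is assumed:

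| Assumed n per arm | Chance half-width ≤ 3.2 | Half-width at SD 5 |
|---|---|---|
| 4 | 7.8% | 8.0 |
| 9 | 30.2% | 3.8 |
| 13 | 66.4% | 3.0 |
| 17 | 92.6% | 2.6 |

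**4. Does the model as listed give visit-specific estimates by arm?**

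Write the listed terms as main effects: log2 expression = μ + treatment + time + tissue + participant intercept + error. The contrast of Week 4 against baseline in lesional skin, within one arm, is time(Week 4) − time(baseline). The treatment and tissue terms cancel, so all three arms receive the same fold-change. Arm-specific fold-changes at any visit need a treatment-by-time interaction. Lesional estimates kept separate from non-lesional ones need tissue in that interaction. SAP 5.2.1 states neither, and the visible part of 5.2.2 does not either.

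**The case against.** The strongest reply is that the early tissue is not excluded. Time Point is in the model, the contrasts and correlations in SAP 5.2.1 name no visit, and SAP 5.1 promises estimates and 95% CIs for the biomarker endpoints. Only Week 16 is expressly confined to listings (SAP section 6). Section 6.2.1 is headed as a primary analysis, so Week 12 could be the headline and not the whole. SAP Table 1 places the RNA analyses in a supplementary biomarker SAP, and parts of 5.2.2 and the marker list in 6.2 are blacked out. The markers still visible in 6.2 (thickness, Ki67, K16) belong to an endpoint without multi-visit wording.

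Much of this stands. A reader might infer that the Week 2 and Week 4 biopsies will go unreported. The documents do not show that; they show only that the visible SAP prespecifies no output for them. The supplementary SAP may settle part of the gene-expression endpoint. It is described as covering RNA, however, and IHC is not RNA. The Week 12 line in 6.2.1 is itself unredacted.

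A reader might also infer that 6.1.1 and 6.1.2 are wrong. They are not: the primary endpoint names no intermediate visit and its population is built on baseline and Week 12 data, so Week 12 is a legitimate primary time point.

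Finally, it is tempting to argue that Week 12 tissue merely reflects cleared skin. In Phase 2b, Week 12 IGA response was 44.5% on 200 mg and 27.8% on 100 mg, so most participants were not responders. Protocol 8.1.2 also samples cleared sites deliberately, to assess molecular clearance. Nor can Week 4 alone show that markers move first, since 200 mg IGA had improved until that same week. The case for the earlier visits rests on the endpoint definitions and on matching tissue to clinical results at the same visit.

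**Conclusion.** The point holds as a mismatch between SAP 6.2.1 and SAP 3.2 for two secondary endpoints. In the visible SAP, up to 51 of 102 required post-baseline lesional biopsies (50%), plus any Week 2 samples, have no prespecified fold-change output for endpoints whose definitions call for several visits. This assumes full sampling of 51 participants and that 6.2.1 governs the T-cell and dendritic-cell markers, which cannot be seen in the redacted list. Part of the gene-expression gap may be closed by the supplementary biomarker SAP.

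The consequence is for prespecification and reporting. Sample size is unaffected, and no error rate is involved because no hypothesis testing is planned. It should be corrected, since the tissue is already scheduled and bears directly on the mechanism question.

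**What to change.** - **SAP 6.2.1.** Change the summary to: *fold-change from baseline in lesional skin at Weeks 2 (where sampled), 4 and 12, with n per visit; Week 12 is the main time point.* For RNA outputs, a cross-reference to the supplementary biomarker SAP would serve if that document names the visits.
- **SAP 6.1.1 and 6.1.2.** No correction needed. Weeks 2 and 4 could be added as supportive summaries for the eight primary genes.
- **SAP 5.2.1 and 5.2.2.** State the treatment-by-time interaction, with tissue, from which visit-specific contrasts by arm are taken.
- **Inclusion.** State that a Week 12 sample is not required for the Week 2 and Week 4 summaries, so that a participant with baseline and Week 4 tissue but no Week 12 biopsy still counts at Week 4.

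The cost is SAP wording and extra table columns; no new data are collected. The downsides are more estimates without multiplicity control, which SAP 5.1 already accepts, and possibly wide intervals at Week 2, which reporting n per visit will make plain.

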6.3. Efficacy Endpoints

6.3.1. NRS4 for Severity Response

- Summary: Proportion of subjects with NRS4 for severity response at Weeks 4, 8 and 12;
- Population: Subjects from the FAS with a baseline NRS score for severity ≥ 4 ;
- Statistical Method: Descriptive (n, %), 95% CI and difference from placebo. Visit windows will be used as described in Appendix 2;
- Missing Data: Missing data arising due to subject dropout are considered “non-response”.

6.3.2. IGA Response

- Summary: Proportion of subjects with IGA score of clear (0) or almost clear (1) and a reduction from baseline of ≥ 2 points at Weeks 2, 4, 8 and 12;
- Population: Subjects from the FAS with a baseline IGA score ≥ 2 ;
- Statistical Method: Descriptive (n, %). Visit windows will be used as described in Appendix 2;
- Missing Data: Missing data arising due to subject dropout are considered “non-response”.

6.3.3. EASI50, EASI75 and EASI90 Response

- Summary: Proportion of subjects with EASI response at Weeks 2, 4, 8 and 12;
- Population: FAS;
- Statistical Method: Descriptive (n, %). Visit windows will be used as described in Appendix 2;
- Missing Data: Missing data arising due to subject dropout are considered “non-response”.

6.3.4. Change from Baseline in BSA%

- Summary: Change from baseline at all scheduled visits;
- Population: FAS;
- Statistical Method: Descriptive (LSmean, SD, mean difference, SE, 95% CI, median, Q1, Q3);
- Missing Data: Observed Data.

CCI [REDACTED]
[REDACTED]
[REDACTED]
[REDACTED]
[REDACTED]
[REDACTED]
[REDACTED]

C

6.4.2. Night Time Itch Scale

- Summary: Change from baseline in Night Time Itch Scale at all scheduled visits;
- Population: FAS;
- Statistical Method: Descriptive (mean, SD, median, Q1, Q3);
- Missing Data: Observed data.

CCI

6.5. PK Endpoints

PK concentration data for PF-04965842 and its metabolites will be summarized through appropriate data tabulations, descriptive statistics, and graphical presentation. A population PK model will be developed for the purpose of estimating PK parameters. Additional details of the methodology will be captured in a separate modeling plan and the results will also be reported separately.

6.6. Subset Analyses

Summary statistics for co-primary endpoints will be presented by subgroups below.

- Age (years) group; (<40 , ≥ 40);

- Race (White, Black or African-American, Asian, Other¹);
- Baseline disease severity (moderate, severe).

Point estimates and 95% confidence intervals will be derived from MMRM models as described in [Section 5.2.1](#).

The primary purpose of the subgroup analyses is to check for consistency of results across subgroups, to make sure overall results are not being driven by some subset of subjects.

Graphical display (eg, forest plots) of the differences between treatment groups will be presented. There is no intention to have any specific inference within subgroups.

6.7. Baseline and Other Summaries and Analyses

6.7.1. Baseline Summaries

Demographics, medical history, primary diagnosis, history of prior AD treatments and disease characteristics will be summarized by treatment group according to CaPS.

6.7.2. Study Conduct and Subject Disposition

Subjects' evaluation, disposition and discontinuation will be summarized according to CaPS.

6.7.3. Study Treatment Exposure

Subjects were expected to take 2 tablets of 100 mg per day (on a QD schedule) during the 12 weeks treatment period. The study drug compliance is defined as:

Drug compliance (%) = $100 \times \text{Actual number tablets taken} / \text{Expected number of tablets}$,

where

Actual number tablets taken = Total number of dispensing tablets [at Week 0 (Day 1), 4, and 8] – Total number of return tablets (at Weeks 4, 8, and 12);

Expected number of tablets = $2 \times \text{Days of treatment duration} (\text{Last treatment date} - \text{First treatment date} + 1)$.

The study compliance (%) and study durations (days) will be summarized for each treatment group.

¹ For purposes of analysis, Other will comprise the categories of American Indian or Alaska Native, Hawaiian or Other Pacific Islander, Multi-Racial and any other category reported on the CRF.

